3.3 OUTCOME MEASURES

3.3.1 Primary Outcome Measure

- Mean change in ETDRS visual acuity at 24 months (week 92 – week 107) from Day 0.

3.3.2 Secondary Outcome Measures

- Incidence and severity of adverse events (ocular and non-ocular).
- Total number of intravitreal injections required during each year of the study period (week 52, week 104, and week 156). In a separate proof of concept analysis, the number of intravitreal injections in the TREX and GILA cohorts over the 36-month study period will be compared with that of the other two cohorts ($p = 0.20$)
- Total number of office visits and imaging studies performed during each year of the study period (week 52, week 104, and week 156).
- Mean change in central foveal thickness per SDOCT from randomization to 12 months (week 46 – week 57), randomization to 24 months (week 92 – week 107), and randomization to 36 months (week 156).
- Percentage of eyes gaining or losing 3 lines of vision or more and 1 line of vision or more at 6 months (week 22 – week 29), 12 months (week 46 – week 57), 18

months (week 70 – week 85), 24 months (week 92 – week 107), and 36 months (week 156) from Day 0.

- Noninferiority comparison (margin of 9 letters) of mean change in ETDRS vision from Day 0 to 24 months (week 92 – week 107) between the three study groups.
- The percentage of eyes which show progression of proliferative diabetic retinopathy requiring panretinal photocoagulation and/or pars plana vitrectomy over the 36-month study period.
- The percentage of eyes in the TREX and GILA cohorts who are eligible to begin the extension phase after 4 treatment visits.
- For TREX and GILA Cohorts, the time to achieve a “Secondary or Tertiary Baseline” retinal thickness.
- Percentage of eyes in each cohort that have shown a two-step change (increase and decrease) in diabetic retinopathy at 24 months and 36 months from day 0.

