Because of these and other realities, alternatives to chronic, monthly dosing need to be explored. The DRCR Network has employed a “4-2-7” strategy in which patients receive 4 mandatory doses, followed by PRN dosing based on clinical response. In this proposal, an initial loading dose of 4 injections is proposed because much of the vision gains in RISE and RIDE were attained during the first 120 days. By only extending the interval by 2 weeks at each successful visit, it is postulated that the gains achieved early on may be maintained without aggressive recurrence. Once a patient reaches an interval that limits the control of disease activity, their recurrence is likely to be mild or even subclinical. At one year, it is likely that there will be a wide variety of dosing intervals in the cohort, based on disease activity, addition of panretinal photocoagulation, or other factors. What is unknown is how the visual outcomes with a “treat and extend” protocol will compare to the RISE and RIDE trials.

Rationale for Guided Laser photocoagulation

Since the publication of the Early Treatment Diabetic Retinopathy Study (ETDRS), macular laser photocoagulation has been vital in the management of DME. Because of the retina community’s positive experience with macular laser, it is likely that many clinicians will utilize some form of combination therapy in clinical practice. Recent data published by the Diabetic Retinopathy Clinical Research Network’s (DRCR.net) protocol I offers some direction for inclusion of laser in this protocol. Although faithful treatment with ranibizumab alone offered the best final visual outcome, the number of injections required at long-term follow-up were less in patients that received macular laser sometime during their treatment. In Protocol I, patients who received deferred laser had better visual outcomes compared to those receiving laser at entry. It is felt that by treating initially with ranibizumab caused some resolution of the macular edema, which allowed for better treatment effect with lower laser power settings, thereby minimizing laser-induced scotomas.

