4.1.3 Exclusion Criteria

Subjects who meet any of the following criteria will be excluded from this study:

General Exclusion Criteria

- Pregnancy (positive urine pregnancy test) or lactation.
- Premenopausal women not using adequate contraception. The following are considered effective means of contraception: surgical sterilization or use of oral contraceptives, barrier contraception with either a condom or diaphragm in conjunction with spermicidal gel, an IUD, or contraceptive hormone implant or patch.
- Any other condition that the investigator believes would pose a significant hazard to the subject if the investigational therapy were initiated
- Participation in another simultaneous medical investigation or trial

Ocular Exclusion Criteria

Prior Ocular Treatment

- History of active proliferative diabetic retinopathy in the study eye on clinical exam
- History of vitrectomy surgery, submacular surgery, or other intraocular surgical intervention for diabetic macular edema in the study eye
- Any previous intravitreal drug delivery (e.g., intravitreal corticosteroid injection, anti-VEGF drugs including ranibizumab, or device implantation) in the study eye within 90 days of the screening visit.
- History of prior laser macular photocoagulation more than 90 days prior to screening will be eligible for study inclusion. However, if the investigator does not feel that additional laser photocoagulation can be safely performed or would benefit the patient, then the eye in consideration will be excluded.

- Evidence of vitreomacular interface abnormality or epiretinal membranes which may be responsible for macular edema

Concurrent Ocular Conditions

- Any concurrent intraocular condition in the study eye (e.g., cataract or macular degeneration) that, in the opinion of the investigator, could either:

Require medical or surgical intervention during the 24-month study period to prevent or treat visual loss that might result from that condition; or if allowed to progress untreated, could likely contribute to loss of at least 2 Snellen equivalent lines of BCVA over the 24-month study period.

- Active intraocular inflammation (grade trace or above) in the study eye
- Current vitreous hemorrhage in the study eye
- History of rhegmatogenous retinal detachment or macular hole (Stage 3 or 4) in the study eye
- Active infectious conjunctivitis, keratitis, scleritis, or endophthalmitis in either eye
- Aphakia in the study eye

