4.4 CONCOMITANT AND EXCLUDED THERAPIES

Subjects may continue to receive all medications and standard treatments administered for their conditions at the discretion of their treating physician except non-ranibizumab intraocular therapies for DME, including corticosteroids and other anti-VEGF agents.

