4.6 SUBJECT DISCONTINUATION

Subjects have a right to withdraw from the study at any time.

The subject may be withdrawn from the study for any reason: if it is in the best interest of the subject, intercurrent illness, adverse events, or worsening condition. Palmetto Retina Center, LLC or [name] may request the withdrawal of a subject because of protocol violations, administrative reasons, or any other valid and ethical reasons.

If a subject discontinues from the study, he or she will not be allowed to re-enter the study.

Reasons for subject discontinuation may include, but are not limited to, the following:

- Sensory rhegmatogenous retinal detachment or Stage 3 or 4 macular hole
- Investigator determination that it is not in the best interest of the subject to continue participation
- Pregnancy
- Need for anti-VEGF therapy other than ranibizumab in the study eye, unless as a part of the prospective investigational study design
- SAE
- Any other safety concerns

In the event of an adverse event in the study eye that is considered by the investigator to be severe in intensity, serious consideration should be given to discontinuing the subject from the study.

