4.8.4 Missing Data

Analyses of efficacy and safety will be based on available cases, without imputation for missing values.

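### The two-step retinopathy outcome has no rule for eyes already given panretinal laser or vitrectomy for proliferative disease, so an eye that progressed and was treated may be scored as unchanged or improved, or drop out.

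*Combined protocol and SAP*

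**What the plan says.** Sections 2.2, 3.3.2 and 4.8.3 give the outcome in the same terms: "Percentage of eyes in each cohort that have shown a two-step change (increase and decrease) in diabetic retinopathy at 24 months and 36 months", measured from Day 0. None of the three names a grading scale or mentions treatment received before the reading.

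The same lists carry a separate outcome, the share of eyes with "progression of proliferative diabetic retinopathy requiring panretinal photocoagulation and/or pars plana vitrectomy over the 36-month study period". It is cumulative, and nothing links it to the two-step percentages.

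Other sections bear on whether treated eyes reach the reading:

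- Section 3.2 expects dosing intervals at one year to vary "based on disease activity, addition of panretinal photocoagulation, or other factors".
- Section 4.4 states that "Subjects may continue to receive all medications and standard treatments administered for their conditions at the discretion of their treating physician". Its only exception is non-ranibizumab intraocular therapy for DME.
- Section 4.6 lists neither procedure as a reason to discontinue, but it allows withdrawal "if it is in the best interest of the subject, intercurrent illness, adverse events, or worsening condition".
- Section 4.1.3 excludes "History of active proliferative diabetic retinopathy in the study eye on clinical exam".
- Section 4.8.4 states: "Analyses of efficacy and safety will be based on available cases, without imputation for missing values".

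**The concern.** Panretinal photocoagulation and vitrectomy are given to control proliferative disease. An eye that progresses, is treated and is quiet at month 24 is then read in its treated state. Under the definition as written, that eye may be absent from the increase percentage and may even appear in the decrease percentage. A reader would take the latter as a benefit of the injection regimen, when it reflects the added procedure. If the eye cannot be graded, or the subject has been withdrawn, the available-case rule removes it, and the failure is again missing from the numerator.

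This matters for comparing cohorts. Section 3.1 lets the TREX and GILA intervals reach 12 weeks in year one and 16 weeks in year two. Retinopathy progression is an outcome on which less frequent dosing could do harm. Losing progressed eyes from the count would tend to hide such harm where most eyes progress.

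**Working it through.** **Figures available.** The documents give no expected rate, power or alpha for this outcome, so there is no plan figure to reproduce. Cohort sizes are 30 (Monthly), 60 (TREX) and 60 (GILA), from sections 3.1 and 4.2. The number of eyes treated for proliferative disease before a reading is not given; the values below are assumptions.

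**Step 1: can a treated eye reach the reading?** Section 3.2 expects panretinal laser and section 4.4 permits standard treatments. Section 4.6 does not require either procedure to end participation. Section 4.5.1 schedules fundus photography at months 24 and 36 in Monthly and TREX, and about every three months in GILA, with no exemption for treated eyes. So a treated eye can be graded. It can also be withdrawn or ungradable, and then section 4.8.4 leaves it out.

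**Step 2: does any rule classify it?** Sections 2.2, 3.3.2 and 4.8.3 contain none. Section 4.8.1 assigns only exploratory models to the remaining secondary outcomes. The laser/vitrectomy outcome counts the procedures over 36 months but does not adjust the two-step percentages, and it does not give a 24-month figure.

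**Step 3: one eye.** The shift is 1/n: 1/30 = 3.3 points in Monthly, and 1/60 = 1.7 points in TREX or GILA.

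**Step 4: several eyes.** If k treated eyes all belong in the increase count and all are graded as not worsened, the increase percentage is understated by k/n.

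- TREX or GILA, k = 2 to 6 (assumed): 2/60 = 3.3 points to 6/60 = 10.0 points.
- Monthly at the same shares, k = 1 to 3: 1/30 = 3.3 points to 3/30 = 10.0 points.

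These are upper bounds. Any treated eye that is still graded as worsened, or that had not worsened by two steps, reduces them.

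**Step 5: worked example (assumed).** In a cohort of 60, 6 eyes truly worsen by two steps, and 3 of them are treated before the reading.

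| Handling of the 3 treated eyes | Increase reported |
|---|---|
| Graded as unchanged | 3/60 = 5.0% |
| Graded as a two-step decrease | 3/60 = 5.0%, with the decrease percentage raised by 3/60 = 5.0 points |
| Ungradable or withdrawn, so left out | 3/57 = 5.3% |
| Counted as an increase | 6/60 = 10.0% |

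**Step 6: cohort differences.** Let p1 and p2 be the true increase rates, and f the fraction of worsened eyes graded as not worsened. With the same f in both cohorts, the observed difference is (1 - f)(p1 - p2), so f = 1/2 halves it. With different fractions it is (1 - f1)p1 - (1 - f2)p2, which can shift either way.

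**The case against.** The strongest reply is that misclassification depends on a scale the documents do not name. A scale that scores laser scars or a vitrectomised eye as advanced disease would reduce the problem. This stands: the concern is conditional, and the missing scale is part of what needs repair.

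A reader might infer from the exclusion of active proliferative disease that any eye treated for it on study has by definition worsened, and by two steps. The documents do not support that. Section 4.1.3 does not clearly exclude quiescent, previously treated proliferative disease, and no criterion excludes earlier panretinal laser. The neighbouring outcome's wording, progression of proliferative disease, is compatible with some such eyes at entry. An eye that has worsened has also not necessarily moved two steps.

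A reader might also infer that all treated eyes stay and are graded. Section 4.6 allows withdrawal for a worsening condition, and its list of reasons is not exhaustive, so retention is possible but not assured. Withdrawal does not rescue the outcome, because the available-case rule then drops the eye.

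It can fairly be said that treated progression is reported in its own outcome and that an as-graded percentage is a legitimate measure. Both are true. But the separate count is not tied to the two-step figures, does not correct the 24-month reading, and leaves the decrease percentage open to a treatment effect that is not the regimen's.

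Finally, the trial is open-label and gives no criteria for either procedure, so a composite brings unmasked treatment decisions into the outcome. That is a real cost of the fix.

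**Conclusion.** The point holds as a conditional weakness in the outcome definition. As written, an eye that progressed and was treated before month 24 or 36 can be scored as unchanged or improved, or can leave the analysis, and nothing else in the plan corrects the two-step percentages. To state as fact that the increase percentage is understated would go too far, because that depends on the unnamed scale.

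The size is unknown. The range of 3.3 to 10 points for 2 to 6 of 60 eyes rests on an assumed number of treated eyes and on all of them being graded as not worsened.

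The consequence is limited. This is an exploratory secondary outcome, and the primary visual acuity analysis is untouched. The dosing contrast bears mainly on the 24-month reading, because from week 104 all three cohorts follow the same PRN rule (section 3.1). The correction is still worth making, because it is cheap and removes a source of bias.

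**What to change.** In sections 2.2, 3.3.2 and 4.8.3:

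1. Name the grading scale.
2. At 24 and 36 months, report the percentage of eyes with a two-step increase, or with panretinal photocoagulation and/or vitrectomy for proliferative retinopathy since Day 0 and on or before the time point. Include treated eyes whose later grade is missing.
3. State that such an eye is not counted as a two-step decrease.
4. Give the as-graded percentages beside the composite, with the denominator for each cohort.

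This changes outcome classification only, not treatment. It costs a short addition to the definition and one extra table; the procedures already have to be recorded for the neighbouring outcome.

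The plan should state the downsides. Some treated eyes may have worsened by less than two steps, including any with quiescent treated proliferative disease at entry. Treatment decisions are open-label. Treated eyes enter without a grade while untreated eyes without one remain excluded, which is why the denominators should be shown. The as-graded table shows how many eyes the rule changes. The rule should be fixed before the 24-month data are analysed.

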3.4 SAFETY PLAN

The safety assessments to be conducted for this study are listed in Section 5 and Appendix A.

The safety and tolerability of intravitreal ranibizumab injections have been investigated in previous Phase I, I/II, III, and IIIb studies in AMD. Potential safety issues associated with the route of administration or the pharmacology of ranibizumab in the study population include decreased BCVA, intraocular inflammation, intraocular infection, transient and/or sustained elevation of intraocular pressure (IOP), cataract development or progression, retinal or intravitreal hemorrhage, macular edema, retinal break or detachment, and arterial thromboembolic events (ATEs). Safety will be assessed by visual acuity, ophthalmic examinations including intraocular measurements, fluorescein angiograms, adverse events and vital signs.

To minimize the risks of intraocular injections, all injections will be performed employing surgical sterile techniques as described in Appendix B. Following each injection, subjects will have a retinal examination either by indirect ophthalmoscopy or checking subject’s ability to see (at investigator’s discretion) to ensure that there is a good perfusion of retinal vessels.

Study drug administration will be held for subjects who experience certain ocular events or infection events. In the event any subject develops an adverse event in the study eye that is considered by the physician to be severe in

intensity, serious consideration should be given to withdrawing the subject from the study.

All adverse events will be reviewed by the PI on an ongoing basis.

3.5 COMPLIANCE WITH LAWS AND REGULATIONS

Drug and Administration (FDA) Good Clinical Practices (GCPs), and local ethical and legal requirements.

4. MATERIALS AND METHODS

4.1 SUBJECTS

4.1.1 Subject Selection

150 eyes from approximately 3 sites in the United States will be enrolled. Eligible subjects who have provided informed consent will be screened for eligibility before the initiation of any study procedures. Screening evaluations may be performed at any time within the 14 days preceding Day 0. These subjects must have center involved diabetic macular edema, with evidence of activity seen on SD-OCT.

(See attached Appendix A, the study flow chart, for screening assessments.)

4.1.2 Inclusion Criteria

Subjects will be eligible if the following criteria are met:

- Ability to provide written informed consent and comply with study assessments for the full duration of the study
- Age \geq 18 years of age
- Patient-related considerations
- For sexually active women of childbearing potential, agreement to the use of an appropriate form of contraception (or abstinence) for the duration of the study
- Although no birth control method is 100% effective, the following are

considered effective means of contraception: surgical sterilization, use of oral contraceptives, barrier contraception using either a condom or diaphragm with spermicidal gel, an intrauterine device, or contraceptive hormone implant or patch. A patient's primary care physician, obstetrician, or gynecologist should be consulted regarding an appropriate form of birth control.

- Ability and willingness to return for all scheduled visits and assessments

Disease-related considerations

- The presence of center-involving diabetic macular edema on clinical exam and SD-OCT
- Best corrected visual acuity in the study eye, using ETDRS testing, between 20/25 and 20/320 (Snellen equivalent), inclusive.
- Clear ocular media and adequate pupillary dilation to permit good quality fundus imaging.

4.1.3 Exclusion Criteria

Subjects who meet any of the following criteria will be excluded from this study:

General Exclusion Criteria

- Pregnancy (positive urine pregnancy test) or lactation.
- Premenopausal women not using adequate contraception. The following are considered effective means of contraception: surgical sterilization or use of oral contraceptives, barrier contraception with either a condom or diaphragm in conjunction with spermicidal gel, an IUD, or contraceptive hormone implant or patch.
- Any other condition that the investigator believes would pose a significant hazard to the subject if the investigational therapy were initiated
- Participation in another simultaneous medical investigation or trial

Ocular Exclusion Criteria

Prior Ocular Treatment

- History of active proliferative diabetic retinopathy in the study eye on clinical exam
- History of vitrectomy surgery, submacular surgery, or other intraocular surgical intervention for diabetic macular edema in the study eye
- Any previous intravitreal drug delivery (e.g., intravitreal corticosteroid injection, anti-VEGF drugs including ranibizumab, or device implantation) in the study eye within 90 days of the screening visit.
- History of prior laser macular photocoagulation more than 90 days prior to screening will be eligible for study inclusion. However, if the investigator does not feel that additional laser photocoagulation can be safely performed or would benefit the patient, then the eye in consideration will be excluded.

- Evidence of vitreomacular interface abnormality or epiretinal membranes which may be responsible for macular edema

Concurrent Ocular Conditions

- Any concurrent intraocular condition in the study eye (e.g., cataract or macular degeneration) that, in the opinion of the investigator, could either:

Require medical or surgical intervention during the 24-month study period to prevent or treat visual loss that might result from that condition; or if allowed to progress untreated, could likely contribute to loss of at least 2 Snellen equivalent lines of BCVA over the 24-month study period.

- Active intraocular inflammation (grade trace or above) in the study eye
- Current vitreous hemorrhage in the study eye
- History of rhegmatogenous retinal detachment or macular hole (Stage 3 or 4) in the study eye
- Active infectious conjunctivitis, keratitis, scleritis, or endophthalmitis in either eye
- Aphakia in the study eye
- Intraocular surgery (including cataract surgery) in the study eye within 3 months preceding Day 0
- Uncontrolled glaucoma in the study eye (defined as IOP \geq 30 mmHg despite treatment with anti-glaucoma medication)
- History of glaucoma-filtering surgery in the study eye
- History of corneal transplant in the study eye
- History of pars plana vitrectomy

Concurrent Systemic Conditions

- Any history of use of systemic anti-VEGF agents
- Uncontrolled blood pressure (defined as systolic $>$ 180 mmHg and/or diastolic $>$ 110 mmHg while patient is sitting)
 - If a patient's initial reading exceeds these values, a second reading may be taken 30 or more minutes later. If the patient's blood pressure needs to be controlled by antihypertensive medication, the patient can become eligible if medication is taken continuously for at least 30 days prior to Day 0.
- Atrial fibrillation not managed by patient's primary care physician or cardiologist within 3 months of screening visit
- Women of childbearing potential not using adequate contraception (as defined in the inclusion criteria).
 - A woman is considered not to be of childbearing potential if she is postmenopausal, defined by amenorrhea for at

least 1 year in a woman > 45 years old; or has undergone hysterectomy and/or bilateral oophorectomy.

- History of stroke within the last 3 months of screening visit
- History of other disease, metabolic dysfunction, physical examination finding, or clinical laboratory finding giving reasonable suspicion of a disease or condition that contraindicates the use of an investigational drug or that might affect interpretation of the results of the study or renders the patient at high risk for treatment complications
- Current treatment for active systemic infection
- Active malignancy
- History of allergy to fluorescein, not amenable to treatment
- Inability to obtain fundus photographs or fluorescein angiograms of sufficient quality to be analyzed and graded by the reading center
- Inability to comply with study or follow-up procedures
- Previous participation in any studies of investigational drugs within 1 month preceding Day 0 (excluding vitamins and minerals)

